2.2 Study Objectives and Endpoints

Objectives:

Primary:

To evaluate whether 26 weeks of “one stop” integrated health services delivered in a mobile unit, supported by peer navigation, improves use of MOUD and increases use of PrEP, as measured at 26 weeks among people without HIV, when compared to 26 weeks of peer navigation to similar health services available at community-based agencies.

Secondary:

- 1) To evaluate whether 26 weeks of “one stop” integrated health services delivered in a mobile unit, supported by peer navigation, compared to 26 weeks of peer navigation to similar health services available at community-based agencies:
 - a) improves use of MOUD at 52 weeks
 - b) increases rates of viral suppression among people living with HIV at 26 and 52 weeks
 - c) increases use of PrEP among people without HIV at 26 and 52 weeks
 - d) decreases opioid and polysubstance use at 26 and 52 weeks
 - e) decreases prevalence of bacterial STIs at 26 and 52 weeks
 - f) decreases fatal and non-fatal overdose events by 26 and 52 weeks
 - g) increases the proportion of participants with undetectable HCV RNA at 26 and 52 weeks among those with chronic HCV infection at enrollment

- h) decreases HCV incidence at 52 weeks, for those who are HCV negative at enrollment
- 2) To evaluate whether 26 weeks of “one stop” integrated health services delivered in a mobile unit, supported by peer navigation, increases MOUD use, viral suppression, and PrEP use at 26 and 52 weeks compared to Enrollment
- 3) To evaluate whether 26 weeks of peer navigation to similar health services available at community-based agencies increases MOUD use, viral suppression, and PrEP use at 26 and 52 weeks compared to Enrollment
- 4) To document the prevalence of seropositivity for SARS-CoV-2 at baseline, 26 and 52 weeks
- 5) To document the impact of the COVID-19 epidemic on participants’ experiences of seeking, obtaining and/or maintaining health services, housing, food security and drugs
- 6) To evaluate implementation of “one-stop” integrated health services using a mobile unit, supported by peer navigation, across study sites to identify mechanisms at multiple levels to:
 - a) Guide real-time improvements and refinements in the conduct of the study to ensure primary and secondary outcomes are met with fidelity
 - b) Examine the quality and process of services delivered in each study arm, particularly as these affect primary and secondary outcomes

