5. GENERAL ANALYSIS METHODS

Participants characteristics at baseline will include the number of subjects with non-missing value (n), plus frequency and percentage for the categorical variables; and mean, median, standard deviation (SD), minimum (min), and maximum (max) for the continuous variables. Baseline is defined as Enrollment visit, except for data collected at screening and not at enrollment visit. For example, opioids data collected at screening visit will be considered as baseline data.

Any deviations from this statistical plan will be described in the final report. Primary and secondary outcomes will be limited to data collected within the allowable visit window for the week 26 and week 52 visits, respectively.

For all outcomes below, “retained” at 26 weeks is defined as having completed the 26-week visit within the allowable window of 126-308 days from enrollment, and “retained” at 52 weeks is defined as having completed the 52-week visit within the allowable window of 309-449 days from enrollment.

[figure not shown]
For MOUD outcomes, biological detection of Buprenorphine (or Norbuprenorphine or Buprenorphine Glucuronide) or Methadone (or EDDP) will be performed via laboratory analysis of plasma and urine samples. Detectable MOUD is defined as a value above the lower limit of quantitation (LLOQ) for any of the medications or metabolites mentioned above, in either plasma or urine.

For PrEP outcomes, the PrEP regimen tested (Truvada or Descovy in DBS, or CAB-LA in plasma) is determined based upon reported PrEP use. If there is no reported PrEP usage, the default regimen is Truvada. Detectable PrEP is defined as a value above the lower limit of quantitation (LLOQ) for the PrEP regimen tested.

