Note: Participants can be non-prevalent (positive tests with tier $< 1:8$) but also not negative for syphilis. Thus, they had syphilis previously, but it is not a prevalent infection.

New syphilis is defined as a positive non-treponemal test and positive treponemal test (regardless of titer value) at a follow-up visit when they were negative at the previous visit.

These outcomes will be modeled and summarized using the same strategy as specified for the primary outcome in section 8 above.

f) Decreases fatal and non-fatal overdose events by 26 and 52 weeks

Outcomes:

- Death, with overdose as cause, collected on or before 26- and on or before 52-week visits, separately.
- Self-report of non-fatal overdose, collected on or before week 26- and on or before 52-week visits, separately.

These outcomes are reported on the SAE log form.

Death, caused by overdose, will be modeled with a time-to-event cox proportional hazards model with treatment arm as a covariate.

Person-time for fatal overdoses will be calculated as follows:

- For those retained (alive) at the visit: time between enrollment and the week 26 or week 52 visit date.
- For those reported deceased by the visit date: time between enrollment and recorded date of death.
- If deceased and no recorded date of death: time between enrollment and the midpoint of last attended visit and termination date.
- Those with no reported death and not retained at week 26 and/or week 52 (or terminated before the visit): use time between enrollment and the last attended visit (or termination date). If no other visit besides enrollment is documented: exclude from the analysis.

Note: Last attended visit can include the enrollment or week 26 visits, an interim visit, or a navigation session

Self-reported non-fatal overdoses will use a Poisson regression model (GLM with log link) with treatment arm as a covariate. We will use the number of reported non-fatal overdoses in the 30 days prior to the respective visit to compare treatment arms.

- g) Increases the proportion of participants with undetectable HCV RNA at 26 and 52 weeks among those with chronic HCV infection at enrollment

Outcome:

- Undetectable HCV RNA at the week 26 and 52 visits (visits analyzed separately) among participants with chronic HCV at enrollment.

The HCV treatment outcome will be modeled and summarized using the same strategy as specified for the primary outcome in section 8 above.

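### The 26-week fatal-overdose analysis is cut at each participant's own week 26 visit (days 126 to 308) instead of at day 182

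*SAP*

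**What the plan says.** Secondary objective 1f in SAP Section 2.2 asks whether the intervention "decreases fatal and non-fatal overdose events by 26 and 52 weeks". Section 10, item 1f turns this into an event tied to visits: "Death, with overdose as cause, collected on or before 26- and on or before 52-week visits, separately".

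Person-time follows the same anchor. For people seen at the visit it is: "For those retained (alive) at the visit: time between enrollment and the week 26 or week 52 visit date". For deaths the rule is: "For those reported deceased by the visit date: time between enrollment and recorded date of death". People who are not retained and have no reported death stop at their last attended visit or at termination. The model is Cox regression with arm as the covariate.

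Section 5 counts a person as retained at week 26 after "having completed the 26-week visit within the allowable window of 126-308 days from enrollment". The week 52 window is days 309 to 449. No fixed calendar cut-off for fatal overdose appears in the SAP.

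Section 10 says overdose outcomes are recorded on the SAE log, and Section 3.1 says SAEs are monitored for all randomized participants.

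**The concern.** A death can be known without a visit, so the visit date is an unnecessary horizon for this endpoint at week 26, when participants remain in the study for about another 26 weeks. Tying the cut to the visit has three consequences.

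- Someone seen on day 130 who dies of overdose on day 170 was alive at the week 26 visit. That person is censored at day 130 in the 26-week analysis, although the death falls within 26 weeks.
- Someone whose week 26 visit is late contributes risk time up to day 308. Intervention and navigation last 26 weeks (Section 2.1), so the 26-week result then includes time after they end. The SAP evaluates durability separately at week 52.
- The rule for deaths refers to a visit date, which a person who died before attending does not have. A death on day 250 with no week 26 visit counts if the programmer uses the end of the window and does not count if day 182 is used. Two programmers could report different numbers of deaths from the same data.

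**Working it through.** **Inputs from the SAP.** Windows of days 126 to 308 and 309 to 449 (Section 5); horizons of 26 and 52 weeks (Section 2.2); intervention length of 26 weeks (Section 2.1). The SAP gives no event count, death rate or power for this endpoint, so there is no figure of its own to reproduce.

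**Inputs assumed.** The distribution of the visit day V within the window, and the overdose death rate. The SAP states neither.

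**Day arithmetic.** 26 × 7 = 182. Earliest visit: 182 − 126 = 56 days short (56/182 = 30.8%). Latest visit: 308 − 182 = 126 days over (126/182 = 69.2%). For week 52: 52 × 7 = 364; 364 − 309 = 55 days short (15.1%) and 449 − 364 = 85 days over (23.4%).

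**Share of deaths misplaced at 26 weeks.** With a small constant hazard:

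- dropped = E[max(182 − V, 0)]/182
- added = E[max(V − 182, 0)]/182, relative to deaths by day 182

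| Visit timing (assumed) | Dropped | Added |
|---|---|---|
| All on day 126 | 30.8% | 0% |
| All on day 154 | 28/182 = 15.4% | 0% |
| Uniform, 126 to 308 | [56²/(2 × 182)]/182 = 4.7% | [126²/(2 × 182)]/182 = 24.0% |
| Triangular, mode 182 | (56/182)(56/3)/182 = 3.2% | (126/182)(126/3)/182 = 16.0% |
| All on day 182 | 0% | 0% |
| All on day 308 | 0% | 69.2% |

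**Effect on the Cox hazard ratio.** Simulated with 4 million participants and an assumed control death rate of 5% per year:

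| True effect | Visit timing | Visit-date cut | Day 182 cut |
|---|---|---|---|
| 0.5 throughout | Uniform 126 to 308, both arms | 0.50 | 0.50 |
| 0.5 throughout | Intervention 126 to 200, control 182 to 308 | 0.50 | 0.50 |
| 0.5 to day 182, then 1.0 | Uniform 126 to 308, both arms | 0.61 | 0.50 |
| 0.5 to day 182, then 1.0 | Days 168 to 196, both arms | 0.51 | 0.50 |

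A hand check of the third row: set control deaths by day 182 to 1. Counted control deaths are (1 − 0.047) + 0.240 = 1.193, and counted intervention deaths are 0.5 × 0.953 + 0.240 = 0.716. With nearly equal person-time the rate ratio is 0.716/1.193 = 0.60, close to the simulated 0.61.

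**In numbers of deaths.** At an assumed 1% to 5% per year in 450 people, deaths by day 182 are 450 × 0.01 × 182/365 = 2.2 to 450 × 0.05 × 182/365 = 11.2. Triangular timing then drops about 0.07 to 0.35 of a death and adds about 0.4 to 1.8.

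**The case against.** The strongest defence is that the definition is explicit and its parts agree: event and person-time both stop at the visit, and Section 5 limits secondary outcomes to data within the visit windows. Days 182 and 364 are a reading of the objective and are not written in the SAP for this endpoint. That stands as far as it goes. The wording "Decreases fatal and non-fatal overdose events by 26 and 52 weeks" nevertheless heads the same item and is naturally read as a fixed horizon.

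A reader might infer that unequal risk periods, or different visit timing by arm, bias the comparison even when true risk is equal. The documents do not support this. The specified Cox model allows unequal follow-up, and counts and person-time move together. In the second simulated row, very different timing by arm left a constant hazard ratio unchanged. Bias needs informative visit timing or an effect that changes over time.

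A reader might also infer that deaths are lost from the trial. They are not: a death left out at 26 weeks still enters the 52-week analysis.

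The 31% and 69% figures place every visit at an edge of the window. Section 3.2 describes a target window inside the allowable one, so they are bounds and not expectations. The range of 126 to 308 days also covers only people retained at week 26; living non-attenders stop at last attended visit or termination.

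The same criticism is weaker at 52 weeks. The SAP shows no systematic ascertainment of deaths after the final visit, and Section 9.1 speaks of events that staff become aware of. Counting logged deaths to day 364 while censoring survivors at an earlier final visit would add post-exit time only for those who died.

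**Conclusion.** The point stands for the 26-week analysis. It does not estimate a 26-week quantity, it moves some known deaths by day 182 out of that analysis, and its cut-off is undefined for people who die without attending.

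The size depends on visit timing and death rates that the SAP does not give. Constant hazard with triangular or uniform timing gives about 3% to 5% of deaths by day 182 dropped, and deaths equal to about 16% to 24% added. The hazard ratio is distorted materially only if the effect wanes after the intervention and visits are widely spread, or if visit timing is related to risk. With a constant effect and non-informative timing it is unchanged, and with visits near day 182 the change is negligible.

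This is a secondary and probably sparse endpoint. The change is worth making because it is cheap, matches the analysis to its objective and removes an ambiguity in the death count.

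**What to change.** In Section 10, item 1f:

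- **26-week analysis.** Count every overdose death on the SAE log through day 182, whether or not the week 26 visit had taken place. Censor everyone else at the earlier of day 182 and the last date known alive, using the week 52 visit or any later contact to establish status at day 182.
- **52-week analysis.** Cap follow-up at day 364. Where the week 52 visit falls earlier, keep censoring at that visit unless vital status is followed in the same way for all participants to day 364.
- Keep the visit windows for endpoints measured at visits.

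The cost is SAP wording and one reprogrammed derivation; the 26-week change needs no new data. Deaths between day 182 and a late week 26 visit would count in the 52-week analysis only. People with an early week 26 visit and no later contact would still be censored at that visit unless a death is logged. That leaves a small asymmetry, and their number should be reported by arm.

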2.3 Randomization

Random treatment-arm allocation will occur at a 1:1 ratio, stratified by study site and by HIV status. Permuted-block randomization will be used to assure balanced groups within each study site and HIV-status subgroup with 30 blocks per site/HIV-status stratum. A list of size 240 [$10 \times (6+8+10)$] would allow each site more than enough randomization slots in case a site is called upon to enroll greater than the projected sample size (approx. $n=80$ HIV negative participants and approx. $n=10$ HIV positive participants per site), or in case of dropouts or randomization errors.

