- h) Decreases HCV incidence at 52 weeks, for those who are HCV negative at enrollment

Outcome:

- HCV antibody positive at the week 52 visit among participants who are HCV antibody negative at enrollment.

HCV incidence will be modeled using Poisson regression (GLM with log link), with treatment arm and site as covariates and person years as an offset. Person time will be computed as the number of years from enrollment to the visit date where infection is first detected for participants with incident HCV infection, and from enrollment to the week 52 visit date (or last available visit) for HCV-negative participants with no incident infection.

2. To evaluate whether 26 weeks of “one stop” integrated health services delivered in a mobile health delivery unit, supported by peer navigation, increases MOUD use, viral suppression, and PrEP use at 26 and 52 weeks compared to enrollment, the following endpoint(s) will be assessed:

- In the intervention arm, change over time in the use of MOUD during the study, comparing documented use of MOUD (biological evidence of MOUD - any detectable medications - and a current MOUD prescription or proof of current receipt of MOUD from a clinic that does not provide individual MOUD prescriptions (e.g., methadone clinics)) at 26 and 52 weeks to documented use of MOUD at enrollment. MOUD use is assumed to be zero at enrollment due to study exclusion criteria. Follow-up endpoints will be defined as alive, retained, and having documented MOUD use.
- Among participants living with HIV at enrollment: change over time in the proportion of people with viral suppression (VL<200 copies/mL), comparing 26 and 52 weeks to enrollment. Follow-up endpoints will be defined as alive, retained, and virally suppressed.

- Among participants who were without HIV at enrollment: change over time in the proportion of people with detectable PrEP drugs in DBS at 26 and 52 weeks compared to enrollment. Follow-up endpoints will be defined as alive, retained, and having detectable PrEP.

The viral suppression outcome will not be modelled. We will report the proportions at enrollment, 26 week and 52-week visits, along with exact Clopper-Pearson 95% confidence intervals using F-quantiles based on the Binomial distribution.

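### HCV incidence (outcome 1h) is defined by antibody alone, so infections acquired shortly before randomization can count as on-study events and pull the rate ratio toward 1

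*SAP*

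**What the plan says.** The objective in SAP Section 2.2 is that the intervention "decreases HCV incidence at 52 weeks, for those who are HCV negative at enrollment". The endpoint, worded the same way in Sections 2.2 and 10, is "HCV antibody positive at the week 52 visit among participants who are HCV antibody negative at enrollment". Antibody status therefore sets both the at-risk group and the event.

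For the analysis, "HCV incidence will be modeled using Poisson regression (GLM with log link), with treatment arm and site as covariates and person years as an offset", so the arm effect is a rate ratio. On exposure, "Person time will be computed as the number of years from enrollment to the visit date where infection is first detected" for cases. Participants without incident infection contribute time to week 52 or their last available visit.

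HCV RNA appears as an outcome only in 1g: "Undetectable HCV RNA at the week 26 and 52 visits (visits analyzed separately) among participants with chronic HCV at enrollment". For 1h the SAP gives no RNA criterion, no rule for enrollees who are infected but antibody negative, no exclusion of early seroconversions and no sensitivity analysis.

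**The concern.** Antibody appears some time after infection. A person infected just before enrollment can test antibody negative that day and antibody positive at week 52. Under 1h that person is at risk at enrollment and a case at follow-up, although the infection predates randomization.

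The intervention cannot prevent such an infection. Allocation is 1:1 (Section 2.3), so these cases are equally frequent in both arms in expectation. Adding the same expected number of events to numerator and denominator moves a ratio toward 1, and a larger sample does not remove this. At stake is the size of the estimated effect on HCV acquisition, and what the reported rate describes: the infections counted come from a period that begins before the person-time does.

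**Working it through.** **Nothing to reproduce.** The SAP gives no HCV incidence, expected rate ratio, number at risk, event count or power for 1h. The size must rest on assumptions.

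**Inputs**
- From the SAP: nominal follow-up T = 52 weeks; 1:1 allocation; rate-ratio model; person-time from enrollment.
- Assumed: antibody lag of w weeks, main range 4 to 10; constant infection hazard before and after enrollment in the control arm; true ratio RR acting in full from randomization.

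**Model.** Seroconversions seen by week 52 come from infections acquired between w weeks before enrollment and T − w weeks after it. Counted events are then proportional to:
- control: w + (T − w) = T
- intervention: w + RR × (T − w)

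Hence:
- observed ratio = [w + RR(T − w)] / T
- share of events predating enrollment = w/T in control and w / [w + RR(T − w)] in intervention

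**Results at T = 52**

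| w (weeks) | Observed, true 0.50 | Observed, true 0.70 | Pre-enrollment share, control | Pre-enrollment share, intervention (true 0.50) |
|---|---|---|---|---|
| 4 | (4 + 24)/52 = 0.54 | (4 + 33.6)/52 = 0.72 | 4/52 = 8% | 4/28 = 14% |
| 8 | (8 + 22)/52 = 0.58 | (8 + 30.8)/52 = 0.75 | 8/52 = 15% | 8/30 = 27% |
| 10 | (10 + 21)/52 = 0.60 | (10 + 29.4)/52 = 0.76 | 10/52 = 19% | 10/31 = 32% |

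Widening the lag to 2 to 12 weeks gives 0.52 to 0.62 for a true 0.50, and 0.71 to 0.77 for a true 0.70.

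**Visit timing.** Section 5 defines retention at week 52 as having "completed the 52-week visit within the allowable window of 309-449 days from enrollment", that is 44.1 to 64.1 weeks. At w = 8 and a true 0.50, the observed ratio is 0.59 at the early end and 0.56 at the late end, so timing matters little.

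**Difference scale.** With control incidence I, the expected rate difference as planned is I × {T − [w + RR(T − w)]}/T = I(1 − RR)(T − w)/T. The pre-enrollment term has cancelled. The remaining factor (T − w)/T reflects infections in the last w weeks that antibody has not yet revealed.

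**Effect of an RNA check at enrollment only.** The ratio becomes RR(T − w)/(T − w) = RR. The control rate, however, now counts T − w weeks of infections over T weeks of person-time, so it is understated by w/T, or 8 to 19%. As planned, early additions and late omissions offset each other in the control arm.

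**Illustration, all inputs assumed:** 100 at risk per arm, 20 infections per 100 person-years, RR 0.5, w = 8. The ratios of counts below sit slightly above the rate ratios because each person is counted once.

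| Definition | Events, control vs intervention | Ratio of counts | SE of log ratio | Power |
|---|---|---|---|---|
| As planned | 18.1 vs 10.9 | 0.60 | √(1/18.1 + 1/10.9) = 0.38 | 26% |
| RNA at enrollment | 15.6 vs 8.1 | 0.52 | √(1/15.6 + 1/8.1) = 0.43 | 32% |
| RNA at both ends | 18.1 vs 9.5 | 0.52 | √(1/18.1 + 1/9.5) = 0.40 | 36% |

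**The case against.** Several points on the other side are sound.

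- **No contradiction.** A reader might infer that the SAP contradicts itself because the objective speaks of HCV-negative people and the endpoint of antibody-negative people. The endpoint is stated identically in both places and is an operational definition of the objective. It has a predictable consequence but is not an inconsistency.
- **RNA may not exist for these participants.** A reader might infer from 1g that enrollment RNA is already in hand. Outcome 1g covers only participants with chronic HCV at enrollment, and the SAP does not show that RNA was run on antibody-negative enrollees. The protocol, not shown, may settle this, but 1h as written would not use such a result.
- **The size is assumed.** At a 4-week lag, 0.50 becoming 0.54 is minor.
- **The correction is not free.** It removes exactly the shares of events in the table. In the illustration the bias on the log scale is about ln(0.60/0.52) ≈ 0.15. Mean squared error is then about 0.38² + 0.15² ≈ 0.17 as planned, against 0.43² ≈ 0.19 after an enrollment-only RNA check. Power still rises, because the contrast is less diluted, but it is low either way.
- **Testing only seroconverters is incomplete.** Already-infected people with no week 52 test stay in the denominator through the last-available-visit rule.

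These points limit the importance of the concern and shape the remedy. They do not remove the pull toward 1, which nothing in the SAP corrects.

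**Conclusion.** The concern holds as a modest, conservative bias in one secondary outcome. For any lag above zero and any true ratio other than 1, the antibody-only definition pulls the planned rate ratio toward 1. The sizes in the first table depend wholly on the assumed lag, constant incidence and an effect that starts in full at randomization.

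Two stronger readings are not supported. The definition does not produce a spurious benefit: pre-enrollment infections are balanced in expectation, and a true ratio of 1 stays at 1. Nor does it affect the trial's main conclusions, since the primary MOUD and PrEP analyses do not use it and the SAP claims no power for 1h. A small correction is worthwhile because it is cheap and the direction of the error is known in advance.

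**What to change.** - For the 1h arm comparison, exclude from both events and person-time those seroconverters whose enrollment sample is HCV RNA positive, using an existing result or a stored sample if one is available. Confirm first that suitable enrollment samples exist and may be used for this purpose.
- Report the antibody-only analysis alongside it. With antibody alone at week 52, late infections are still missed, so the corrected absolute incidence is too low by about w/52 unless RNA is also used at week 52 or person-time is matched to the period in which infections can be detected.
- If samples cannot be tested, keep the definition and state in the SAP and the report that the rate ratio is biased toward 1.

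Cost: a short SAP addition and RNA tests on seroconverters only, about 29 in the illustration (18.1 + 10.9). Under the assumed 4 to 10 week lag, about 8 to 19% of control events are lost and, at a true ratio of 0.50, 14 to 32% of intervention events, with a somewhat wider confidence interval. The SAP should state this loss openly.

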2.5 Sample Size and Power

Sample sizes are chosen to provide sufficient power for both the HIV-related and MOUD-related primary outcomes. By computing sample sizes based on each individual outcome separately and choosing the largest sample size needed for either outcome, high power is achieved for both individual outcomes. Prior work in PWID populations suggests that uptake of MOUD, ART, and PrEP in the control condition will likely be modest;^{1,2} we anticipate 25% uptake of MOUD, 42.5% achieving viral suppression, and 5% uptake of PrEP in the control arm.

Sample sizes are computed to provide 90% power to detect a fifteen-percentage point difference in the proportion of participants achieving success, assuming a 5% type-I error rate (two-sided). A sample of 400 participants is needed to detect a 15-point difference in MOUD use (25% vs. 40%) between the active control and intervention arm at 26 weeks. Approximately 216 people without HIV would be needed to see a 15-point difference in PrEP uptake (5% vs. 20%). To cover both HIV and MOUD outcomes, 400 people without HIV will be needed. Approximately 10% of the study population is expected to be living with HIV – insufficient to accommodate a fully powered subgroup - but because this subgroup is expected to have very different rates of HIV-related success than the people without HIV subgroup, it will be important to analyze these participants separately. To assure 400 people without HIV, the target sample size will be augmented by 50 for a combined total of 450 participants, where 40-50 of those are expected to be people living with HIV.

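### SAP 10, 1h: a yes/no HCV antibody result is fitted by Poisson regression, so the arm comparison runs below its nominal 5% level and loses power, with a small pull of the rate ratio toward 1

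*SAP*

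**What the plan says.** Section 10, item 1h, defines the outcome as "HCV antibody positive at the week 52 visit among participants who are HCV antibody negative at enrollment". Section 2.2 gives the same definition. This is one yes/no result per person.

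The model is then stated: "HCV incidence will be modeled using Poisson regression (GLM with log link), with treatment arm and site as covariates and person years as an offset". No variance estimator is named, so the default model-based Poisson variance applies.

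Time at risk has two rules. For infected participants, "Person time will be computed as the number of years from enrollment to the visit date where infection is first detected". For the others it runs "from enrollment to the week 52 visit date (or last available visit) for HCV-negative participants with no incident infection". There is no rule for the unknown infection date between a negative and a positive test.

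Section 5 defines retention at week 52 by completing the visit within the "allowable window of 309-449 days from enrollment", which is about 0.85 to 1.23 years. The SAP states no HCV incidence, no expected number antibody negative and no power for this endpoint.

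**The concern.** Two features of the outcome do not fit the model.

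First, a participant can become antibody positive only once. With follow-up of nearly equal length, the result is binomial with variance p(1-p), whereas the Poisson model assumes variance p. The model-based variance is therefore too large by about 1/(1-p), and the reported interval is wider than the estimate's own sampling error warrants.

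Second, an infected participant stops being at risk on infection but is credited with time up to the detecting visit. The estimated rate is then too low, and more so in the arm with the higher rate, so a true ratio moves toward 1.

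Both remain with perfect retention and complete testing. What is at stake is the SAP's only between-arm HCV incidence comparison, in a subgroup for which no power is claimed.

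**Working it through.** **Inputs from the SAP.** Binary outcome, Poisson model and time rules (section 10, 1h); test at about one year (section 5); 1:1 allocation (section 2.3); two-sided 5% level (section 2.5, stated there for the sample size and assumed here).

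**Assumed, because the SAP is silent.** Control rate λ of 0.05 to 0.30 per person-year; true rate ratio 0.5, or 1.0 for the null; 180 antibody-negative participants, 90 per arm; one test at T = 1 year. The SAP has no figure of its own to reproduce here.

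**Rate and ratio.** Infection risk by the test is p = 1 - exp(-λT). The planned model estimates p/T in each arm and p1/p0 as the ratio. At λ = 0.30:
- p0 = 1 - exp(-0.30) = 0.2592 and p1 = 1 - exp(-0.15) = 0.1393.
- Control rate 0.2592 instead of 0.30, which is 13.6% too low.
- Ratio 0.1393/0.2592 = 0.537 instead of 0.50.

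**Standard error of the log ratio.** Model-based: sqrt(1/(n·p0) + 1/(n·p1)). True: sqrt((1-p0)/(n·p0) + (1-p1)/(n·p1)). At λ = 0.30, n = 90:
- Model-based: sqrt(0.0429 + 0.0798) = 0.350.
- True: sqrt(0.0318 + 0.0687) = 0.317.
- The model-based value is about 10.5% too large.

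**Level under no effect.** The inflation is 1/sqrt(1-p0), so the actual level is 2·[1 - Φ(1.96/sqrt(1-p0))].

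| Control rate per 100 person-years | Rate understated | Ratio (truth 0.50) | SE too large, ratio 0.5 | Actual level, no effect |
|---|---|---|---|---|
| 5 | 2.5% | 0.506 | 1.7% | 4.4% |
| 10 | 4.8% | 0.513 | 3.4% | 3.9% |
| 20 | 9.4% | 0.525 | 6.9% | 3.0% |
| 30 | 13.6% | 0.537 | 10.5% | 2.3% |

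**Simulation.** 180 participants, five sites, test days within 309-449, arm and site in both models, 2,000 trials per scenario:

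| Control rate per 100 person-years | Null rejection: Poisson | Null rejection: complementary log-log | Power: Poisson | Power: complementary log-log |
|---|---|---|---|---|
| 10 | 2.5% | 4.1% | 15% | 18% |
| 20 | 2.0% | 4.4% | 30% | 38% |
| 30 | 1.8% | 4.6% | 39% | 50% |

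Repeat runs of the same design gave power gaps of 8 to 9 points at 20 per 100 and 11 to 14 at 30. The large-sample formula gives less. At λ = 0.30, Poisson power is Φ((0.621 - 1.96·0.350)/0.317) = 42%, against Φ(0.693/0.351 - 1.96) = 51% for complementary log-log, a gap of 9 points. The same steps at λ = 0.20 (SEs 0.422 and 0.395; 0.422 for complementary log-log) give 32% against 37%, about 5 points.

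**Where the power comes back.** At 30 per 100, the simulated log-scale standard error was 0.358 for Poisson, 0.359 for complementary log-log and 0.318 for Poisson with robust variance. The complementary log-log model regains power by removing the attenuation; the robust variance does so by narrowing the interval. In one run at 10/20/30 per 100, robust Poisson power was 18/39/49%, complementary log-log 18/41/50% and the planned model 14/32/39%.

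**If a week 26 test also dates infections.** At 30 per 100 the rate is understated by 7.1% and the ratio is 0.519, about half the bias in the same direction. Power is 35% and 45% at 20 and 30 per 100, against 39% and 51%.

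**The case against.** The strongest case is that this is immaterial. At 10 per 100 person-years the ratio moves only from 0.50 to 0.513. Even at 30 per 100 the shift is well under a third of a standard error, and the planned 95% interval still covered the true ratio 97 to 98% of the time in simulation. The error is conservative, so it cannot create a false claim. No analysis of this subgroup is well powered under these assumptions: the better model reaches only about half. The outcome, model, covariates and time rules are fully specified and identical in both arms. All of that stands, and it makes the loss of level and power the main point and the bias secondary.

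Four stronger readings are tempting, and the document does not support them:
- That the result is seriously biased toward no effect. The attenuation is small, and p1/p0 is itself a valid risk ratio. It falls short only as the incidence rate ratio that the person-years offset implies.
- That a complementary log-log model would give narrower intervals. On the log scale they are the same width.
- That there is only one test. The outcome definition points to week 52, but the wording on first detection leaves room for an earlier result, and the SAP does not give the testing schedule.
- That the SAP contradicts itself because item 1f states "If deceased and no recorded date of death: time between enrollment and the midpoint of last attended visit and termination date". That is a fallback for an undated death in a Cox model and does not bind item 1h.

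Part of the low rejection rate at 10 per 100 is sparse-data behaviour of the Wald test: the formula gives 3.9%, the simulation 2.5%, and complementary log-log itself only 4.1%.

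**Conclusion.** The model does not fit the outcome, and the error bars are wrong in the conservative direction. Under the assumptions above, the effect is small at 5 per 100 person-years, where power changes by less than one point. At 20 to 30 per 100, null rejection is about 2 to 2.5% instead of 5%, simulated power falls by about 8 to 14 points, the rate is understated by 9 to 14%, and the ratio is about 0.52 to 0.54 instead of 0.50. With a week 26 test the bias roughly halves.

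The direction is secure given model-based variance; the size is not, because incidence and subgroup size are assumed. The pull toward 1 also presumes similar retention by arm. The rule that runs time to the last available visit can shift the ratio either way: at 30 per 100 with 75 per arm, it was 0.59 with retention of 75% control and 90% intervention, and 0.49 with the reverse. That is a separate weakness of the same sentence. This is a secondary endpoint, but the correction is cheap enough to be worth making.

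**What to change.** In section 10, item 1h, replace the Poisson model by a binomial GLM with complementary log-log link for week 52 antibody status, with arm and site as covariates and log(years from enrollment to that test) as offset. The exponentiated arm coefficient is then the incidence rate ratio, and fitted rates by arm come from the same model. If earlier antibody results exist, use the grouped-time form, with one record per tested interval. This restores the nominal level and removes the attenuation, but does not narrow the log-scale interval.

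A smaller alternative is to keep the Poisson model and specify a robust (sandwich) variance. This corrects the interval width and recovers nearly all the power, but leaves the small understatement of the rate and attenuation of the ratio.

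The cost is a small change in SAP wording and about one line of code, with no new data. Under the first option the reported rate will be slightly higher than the Poisson figure.
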